5.2.3 Second Course *

All participants who stop study treatment with SD or better may be eligible for up to an additional 17 cycles (approximately 1 year) of pembrolizumab treatment if they progress after stopping study treatment from the initial treatment phase. This retreatment is termed the Second Course Phase of this study and is only available if the study remains open and the participant meets the following conditions:

Either

- Stopped initial treatment with study treatment after attaining an investigator-determined confirmed CR based on RECIST 1.1, and
 - Was treated with at least 8 cycles of study treatment before discontinuing treatment, and
 - Received at least 2 treatments with pembrolizumab beyond the date when the initial CR was declared

OR

- Had SD, PR, or CR and stopped study treatment after completion of 35 administrations (approximately 2 years) of study treatment for reasons other than disease progression or intolerance

AND

- Experienced an investigator-determined radiographic disease progression by irRECIST 1.1 after stopping initial treatment, and
 - No new anticancer treatment was administered after the last dose of study treatment, and
 - The participant meets all of the safety parameters listed in the inclusion criteria and none of the safety parameters listed in the exclusion criteria, and
 - The study is ongoing

An objective response or disease progression that occurs during the Second Course Phase for a participant will not be counted as an event for the primary analysis of either endpoint in this study.

**Note: patients must have measurable disease at the start of protocol treatment to be eligible for this provision.*

5.3 Concomitant Medications/Vaccinations (allowed & prohibited)

Medications or vaccinations specifically prohibited in the exclusion criteria are not allowed during the ongoing trial. If there is a clinical indication for one of these or other medications or vaccinations specifically prohibited during the trial, discontinuation from trial therapy or vaccination may be required. The final decision on any supportive therapy or vaccination rests with the investigator and/or the participant's primary physician.

5.3.1 Acceptable Concomitant Medications

All treatments that the investigator considers necessary for a participant's welfare may be administered at the discretion of the investigator in keeping with the community standards of medical care. All concomitant medication will be recorded on the case report form (CRF) including all prescription, over-the-counter (OTC), herbal supplements, and IV medications and fluids. If changes occur during the trial period, documentation of drug dosage, frequency, route, and date may also be included on the CRF.

All concomitant medications received within 28 days before the first dose of trial treatment and 30 days after the last dose of trial treatment should be recorded. Concomitant medications administered after 30 days after the last dose of trial treatment should be recorded for SAEs and ECIs as defined in Section 7.2.

5.3.2 Prohibited Concomitant Medications/Therapy

Participants are prohibited from receiving the following therapies during the Screening and Treatment Phase (including retreatment for post-complete response relapse) of this trial:

- Antineoplastic systemic chemotherapy or biological therapy
- Immunotherapy not specified in this protocol
- Chemotherapy not specified in this protocol
- Investigational agents other than pembrolizumab
- Radiation therapy (radiation therapy to a symptomatic solitary lesion or to the brain may be allowed at the investigator's discretion).
- Live vaccines within 30 days prior to the first dose of study treatment and while participating in the study. Examples of live vaccines include, but are not limited to, the following: measles, mumps, rubella, varicella/zoster, yellow fever, rabies, BCG, and typhoid vaccine. Seasonal influenza vaccines for injection are generally killed virus vaccines and are allowed; however, intranasal influenza vaccines (eg, FluMist®) are live attenuated vaccines and are not allowed.

- Systemic glucocorticoids for any purpose other than to modulate symptoms from an event of clinical interest of suspected immunologic etiology. The use of physiologic doses of corticosteroids may be approved after consultation with the Sponsor.

Participants who, in the assessment by the investigator, require the use of any of the aforementioned treatments for clinical management should be removed from the study. All treatments that the Investigator considers necessary for a participant's welfare may be administered at the discretion of the Investigator in keeping with the community standards of medical care.

Medications or vaccinations specifically prohibited in the exclusion criteria are not allowed during the ongoing study. If there is a clinical indication for any medication or vaccination specifically prohibited during the study, discontinuation from study therapy or vaccination may be required. The final decision on any supportive therapy or vaccination rests with the investigator and/or the participant's primary physician. However, the decision to continue the participant on study treatment requires the mutual agreement of the investigator, the Sponsor and the participant.

There are no prohibited therapies during the Post-Treatment Follow-up Phase.

5.3.3 Rescue Medications & Supportive Care

Participants should receive appropriate supportive care measures as deemed necessary by the treating investigator. Suggested supportive care measures for the management of AEs with potential immunologic etiology are outlined along with the dose modification guidelines in Section 5.2.2, [Table 3]. Where appropriate, these guidelines include the use of oral or IV treatment with corticosteroids, as well as additional anti-inflammatory agents if symptoms do not improve with administration of corticosteroids. Note that several courses of steroid tapering may be necessary as symptoms may worsen when the steroid dose is decreased. For each disorder, attempts should be made to rule out other causes such as metastatic disease or bacterial or viral infection, which might require additional supportive care. The treatment guidelines are intended to be applied when the Investigator determines the events to be related to pembrolizumab.

Note: If after the evaluation of the event, it is determined not to be related to pembrolizumab, the Investigator does not need to follow the treatment guidance. Refer to [Table 3] in Section 5.2.2 for guidelines regarding dose modification and supportive care.

It may be necessary to perform conditional procedures such as bronchoscopy, endoscopy, or skin photography as part of evaluation of the event.

5.4 Participant Withdrawal/Discontinuation Criteria

Participants may discontinue study treatment at any time for any reason or be dropped from the study treatment at the discretion of the investigator should any untoward effect occur. In addition, a participant may be discontinued from study treatment by the investigator or the Sponsor if study treatment is inappropriate, the trial plan is violated, or for administrative and/or other safety reasons. Specific details regarding procedures to be performed at study treatment discontinuation are provided in Section 7.1.4 – Other Procedures.

A participant must be discontinued from study treatment but continue to be monitored in the study for any of the following reasons:

- The participant or participant's legally acceptable representative requests to discontinue study treatment
- Confirmed radiographic disease progression, according to irRECIST criteria (outlined in Section 7.1.2.6)
- Any progression or recurrence of any malignancy, or any occurrence of another malignancy that requires active treatment
- Unacceptable adverse experiences as described in Section 5.2.2.
- The participant has a medical condition or personal circumstance which, in the opinion of the investigator and/or sponsor, placed the participant at unnecessary risk from continued administration of study treatment.
- The participant has a confirmed positive serum pregnancy test
- Noncompliance with study treatment or procedure requirements
- Recurrent Grade 2 pneumonitis
- Discontinuation of treatment may be considered for participants who have attained a confirmed complete response (CR), at the PI's discretion. These participants may be eligible for second course treatment described in Section 5.2.3.
- The participant is lost to follow-up
- Completion of 35 treatments with pembrolizumab

Note: The number of treatments is calculated starting with the first dose. Participants who stop will stop pembrolizumab after receiving 17 doses on study. Patients may be eligible for retreatment if they progress after stopping study treatment provided they meet the requirements detailed in Section 5.2.3. Participants may be retreated in the Second Course Phase (Retreatment) for up to an additional 17 cycles (approximately 1 year).

- Administrative reasons

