2.0 TRIAL DESIGN

2.1 Trial Design

This is a Phase II, single center study enrolling 16-28 patients. Patients will be initially enrolled at a single dose level and dose de-escalation of p53MVA will be employed if necessary.

Single arm: *p53MVA* (dose 5.0 x10⁸ pfu) + *pembrolizumab* (anti-PD1 mAb flat dose: 200 mg)

p53MVA and pembrolizumab will be given concurrently in accordance with previous studies that show potential for checkpoint inhibitors in combination with vaccines. The aim is to use pembrolizumab to enhance the activity of the p53MVA vaccine to deliver clinical benefit:

Treatment Schedule:

Week 1 (day 1): p53MVA + pembrolizumab

Week 4: p53MVA + pembrolizumab

Week 7: p53MVA + pembrolizumab

[figure not shown]
Week 10: pembrolizumab

Week 13: pembrolizumab

Week 16: pembrolizumab continuing every 3 weeks up to 35 cycles (105 weeks)*

(Pembrolizumab treatment may be extended beyond 49 weeks if a second course is indicated, see Section 5.2.3)

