More encouraging results were achieved with the anti-PD-1 antibody, Nivolumab. Twenty patients with platinum-resistant ovarian cancer were treated with an intravenous infusion of nivolumab every 2 weeks at a dose of 1 or 3 mg/kg. The best overall response was 15%, which included two patients with durable complete responses (in the 3-mg/kg cohort). The disease control rate in all 20 patients was 45%, median PFS was 3.5 months (95% CI, 1.7 to 3.9 months) and median OS was 20.0 months (95% CI, 7.0 months to not reached) at study termination. However, grade 3 and higher AEs were observed in around 40% of patients [28].

Another ongoing study of PD-1 blockade in ovarian cancer combines Pembrolizumab with weekly paclitaxel (NCT02440425). Paclitaxel induces proinflammatory cytokine secretion and immune cell activation[50]. Another study of Pembrolizumab in ovarian cancer (NCT02054806) reported the following at ASCO 2015: of 26 patients treated, there was one complete response, 2 partial responses and 6 patients with stable disease[51].

This study will evaluate the p53MVA vaccine in combination with a checkpoint inhibitor, pembrolizumab. Subjects must have recurrent, platinum refractory ovarian cancer, with evidence of p53 over expression to be eligible. Patients will receive injections of p53MVA vaccine, for a total of three injections. Patients will be evaluated for toxicity through the first cycle of therapy.

Pembrolizumab will be administered at a standard dose of 200 mg every 3 weeks, for approximately two years (35 cycles). In the case of grade 3 vaccine related toxicity, the dose of p53MVA will be decreased. In the case of pembrolizumab induced immune-mediated adverse events, treatment will be held or permanently discontinued according to the package insert. Pembrolizumab treatment may be extended beyond 49 weeks (17 cycles) if a second course is indicated (see Section 5.2.3). This study will be conducted in compliance with the protocol, Good Clinical Practice (GCP) and the applicable regulatory requirements.

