6.0 TRIAL FLOW CHART

6.1 Study Flow Chart

Trial Period:	Screening Phase		Treatment Cycles								treatment end
			1	2	3	4	to be repeated until week 105				
Treatment Cycle/Title:	Pre study	screening (Visit 2)	5	6	7	8	Safety Follow-up				
Scheduling Window (Days):		-14 to -1		± 5	± 5	± 5	± 5	± 5	± 5	± 5	days post discon
Informed Consent	X										
Inclusion/Exclusion Criteria	X	X									
Demographics and Medical History	X										
prior/concomitant medication review	X										
Review Adverse Events		X	X	X	X	X	X	X	X	X	X
Physical Examination		X	X	X	X	X----as per standard of care-----X					
Vital Signs and Weight		X									
ECOG Performance Status		X									
Pregnancy Test (if indicated)		X									
HIV, active TB and acute hepatitis panel (if indicated)		X									
PT/PTT		X									
CBC with Differential		X	X	X	X	X-----as per standard of care----X					
Comprehensive Serum Chemistry Panel		X	X	X	X	X-----as per standard of care----X					
T3, FT4 and TSH		X	X	X	X	X	X	X	X	X	
Cardiac function (EKG/ECG)		X									
Serum Troponin I, BNP		X		X							
Pembrolizumab			X	X	X	X ^c	X	X	X	X	
p53MVA			X	X	X						
Tumor Imaging (CT or PET/CT)	X				X			X--every 9 weeks--X			
CA-125		X	X	X	X	X	X	X	X	X	
Immunologic Blood Collection ^b			X	X	X	X		*X	*X	*X	

Study Chart Notes: Baseline evaluations must be conducted no more than 14 days before treatment start, except imaging which are permissible up to 30 days prior to initiation of therapy. All treatments/evaluations during/after the treatment phase may be +/- 5 days. *At the discretion of the PI. ^aImaging scans must be obtained prior to cycle 4 of therapy +/- 5 days. Subsequent restaging scans will be obtained after every 3 cycles of treatment. +/- 5 days. ^bAll blood specimens to be collected prior to administration of study agents. Patients with a hemoglobin (Hgb) level < 9g/dL will not undergo further immunologic phlebotomy until the Hgb level has been documented to rise above 9g/dL. ^cAfter completion of the three combined doses of p53MVA + PEM, continued administration of PEM as a single agent may continue up to week 49 (first course). ^dPatients completing Week 49 treatment will have an end of study visit, 1-3 weeks after the last dose of PEM. See Section 5.2.3. on 'Second course' of Pembrolizumab.

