7.1.4 Other Procedures

7.1.4.1 Withdrawal/Discontinuation

When a participant discontinues/withdraws prior to trial completion, all applicable activities scheduled for the final trial visit should be performed at the time of discontinuation. Any adverse events which are present at the time of discontinuation/withdrawal should be followed in accordance with the safety requirements outlined in Section 7.2 - Assessing and Recording Adverse Events. Participants who a) attain a CR or b) complete 24 months of treatment with pembrolizumab may discontinue treatment with the option of restarting treatment if they meet the criteria specified in Section 5.2.3. After discontinuing treatment following assessment of CR, these participants should return to the site for a Safety Follow-up Visit (described in Section 7.1.5.3.1) and then proceed to the Follow-Up Period of the study (described in Section 7.1.5.3.2).

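### The first-course pembrolizumab limit is 35 treatments in most of the protocol, but leftover wording in Sections 5.4, 6.1, 2.1, 4.2.1 and 7.1.5.2 ends it at 17 doses or week 49

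*Combined protocol and SAP*

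**What the plan says.** Among the reasons for ending study treatment, Section 5.4 lists "Completion of 35 treatments with pembrolizumab". The note directly below reads "Participants who stop will stop pembrolizumab after receiving 17 doses on study". Both are current, operative text.

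Places that give the longer limit:
- Section 2.1: "pembrolizumab continuing every 3 weeks up to 35 cycles (105 weeks".
- Section 4.2.1: "for approximately two years (35 cycles".
- Section 5.2.3: patients with SD, PR or CR who stopped on completing treatment qualify for retreatment only after 35 administrations.
- Section 6.1, header: "to be repeated until week 105".
- Section 7.1.4.1: participants who "complete 24 months of treatment with pembrolizumab may discontinue treatment", with the option of restarting later.
- Section 7.1.5.2: up to 35 cycles.
- Section 1.0: participation of at most 24 months.

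Places that give the shorter limit:
- Section 6.1, footnote c: "continued administration of PEM as a single agent may continue up to week 49 (first course". Footnote d then schedules an end of study visit after week 49.
- Section 2.1: "Pembrolizumab treatment may be extended beyond 49 weeks if a second course is indicated, see Section 5.2.3". Sections 4.2.1 and 7.1.5.2 repeat this and equate 49 weeks with 17 cycles.

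On p53MVA, Table 4B resumes vaccination at 2.8×10^8 pfu without a volume. Section 9.4 gives 0.5 mL, stated as 2.2×10^8 pfu, for dose level -1. Table 4B's Grade 3 non-hematologic row covers only events unrelated to the vaccine, whereas Section 4.2.1 calls for a reduction after vaccine-related Grade 3 toxicity.

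**The concern.** For a patient still on drug at week 49, dose 18 is permitted by the Section 5.4 bullet and ruled out by the note under it and by footnote c. One reader would continue treatment. Another would stop and book the end of study visit. The patients concerned are those doing well enough to be on treatment at about a year, and two of them in the same condition could be managed differently.

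The choice also decides access to the Second Course. Section 5.2.3 offers two ways in: a confirmed CR with at least 8 cycles, including at least 2 treatments after the CR was declared, or 35 completed administrations with SD, PR or CR. A patient with SD or PR who is stopped at dose 17 can never meet the second condition, and the first does not apply to her.

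**Working it through.** **Do the stated weeks match the stated doses?** With dosing every 3 weeks from week 1, dose k falls in week 1 + 3(k − 1) and cycle k ends after 3k weeks.

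| Limit | Week of last dose | End of last cycle |
|---|---|---|
| 17 | 1 + 3×16 = 49 | 51 weeks |
| 35 | 1 + 3×34 = 103 | 105 weeks |

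Each number agrees with its own week label: 17 with week 49, and 35 with 105 weeks. These are two coherent schedules, so a miscounted week does not explain the conflict. They differ by 35 − 17 = 18 doses, or 103 − 49 = 54 weeks.

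**Can 35 be a first course of 17 plus a second course?** No. 17 + 17 = 34. Section 5.2.3 also places the 35 administrations before the additional 17 cycles.

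**Which limit agrees with Section 1.0?** One month is 365.25/12/7 = 4.348 weeks, so 24 months is 104.36 weeks.
- 35 cycles: 105/4.348 = 24.1 months, with the last dose in week 103. This matches the 24-month participation and the 24 months of treatment in Section 7.1.4.1.
- 35 + 17 = 52 cycles = 156 weeks = 35.9 months, which is 11.9 months beyond the maximum.
- 17 + 17 = 34 cycles = 102 weeks = 23.5 months.

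**How many patients might reach week 49?** The documents give no distribution of time on treatment, so this is an assumption. Week 49 begins 48 weeks after day 1, or 48/4.348 = 11.04 months. With exponential times and 28 patients:
- Using the nivolumab median PFS in Section 4.2.1 (3.5 months, 95% CI 1.7 to 3.9), 28 × 0.5^(11.04/m) gives 3.1 at m = 3.5, 0.3 at m = 1.7 and 3.9 at m = 3.9.
- Using Section 1.0's average treatment length of 6 to 12 months as the mean, 28 × exp(−11.04/μ) gives 4.4 at μ = 6 and 11.2 at μ = 12.

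**Does the primary analysis depend on the limit?** The Simon design takes response rates of 8% and 25%, 17 then 28 patients, and cut-offs of 2 and 5 responders. The number of pembrolizumab doses is not an input.

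**p53MVA.** At the Section 9.4 concentration of 4.5×10^8 pfu/mL, 0.5 mL contains 2.25×10^8 pfu. A dose of 2.8×10^8 pfu needs 2.8/4.5 = 0.62 mL, and 2.8/2.25 = 1.24, so the Table 4B dose is 24% higher.

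**The case against.** The strongest defence is that no careful reader would be misled. Thirty-five stands in the design section, the stopping bullet, the treatment-period section, the retreatment conditions and the flow chart header, while 17 survives in one garbled note, two footnotes and one repeated sentence. Few patients may reach week 49, and the primary analysis is untouched. Most of this stands. It makes the remedy a correction rather than a new decision, and it keeps the point modest. It does not make the text harmless, because the remnants sit in the discontinuation criteria and the flow chart, which govern what happens at a visit.

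A reader might go further and infer that Section 1.0 favours 17, since 17 + 17 cycles fit within 24 months and 35 + 17 do not. The documents do not support this. Thirty-five cycles alone fill the 24 months, and Section 5.2.3 makes the second course optional and dependent on the study remaining open. The estimated 24-month trial duration does not separate the two limits either. At Section 8.2's rate of one patient every 1.5 months, enrolling 17 patients takes 17 × 1.5 = 25.5 months and enrolling 28 takes 28 × 1.5 = 42 months. The study would run past 24 months under either limit.

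On p53MVA, the volume for 2.8×10^8 pfu is a single division, Section 4.2.1 does direct a reduction for related Grade 3 events, and Section 5.2.2 does not expect reductions to be needed. Those points are correct but minor.

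**Conclusion.** The protocol contradicts itself on an operative treatment rule and should be corrected. The weight of the text identifies 35 treatments as the first-course limit. The 17-dose and week-49 statements are inconsistent with it and cannot be reconciled through the second course.

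The consequence per affected patient is up to 18 doses (54 weeks) of permitted treatment withheld, plus loss of the Second Course for SD or PR. The CR route stays open. On the exponential assumption, the number reaching week 49 could be anywhere from below 1 to about 11 of 28. The low end borrows PFS from another drug and the high end rests on Section 1.0's planning estimate, so the range shows only that the case is plausible.

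It would be wrong to infer that the response-rate result, the error rates or the sample size are compromised, since none of them uses the dose limit. The mismatch between a 24-month maximum and a possible 35.9 months with retreatment is a separate, minor gap in Section 1.0. The p53MVA discrepancies are minor too and could affect only injections 2 and 3.

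**What to change.** In one amendment:
- Section 5.4 note: replace 17 doses with 35 doses.
- Section 6.1, footnotes c and d: refer to dose 35 (week 103; cycle 35 ends at week 105).
- Sections 2.1, 4.2.1 and 7.1.5.2: delete the sentence about treatment beyond 49 weeks, or correct it to refer to treatment after 35 cycles.
- Section 1.0: state that the 24-month maximum excludes the optional second course, which can bring treatment to 52 cycles (35.9 months, plus any gap between courses).
- Table 4B and Section 9.4: use one reduced p53MVA dose and volume, either 2.8×10^8 pfu in 0.62 mL or 2.25×10^8 pfu in 0.5 mL.
- Table 4B, Grade 3 non-hematologic row: make it cover toxicity related to p53MVA, in line with Section 4.2.1.

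The cost is wording only, with no extra patients, procedures or statistical changes. The 18 further doses are already allowed by the bullet in Section 5.4. The change should be in force before any patient reaches week 49.

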5.5 Participant Replacement Strategy

5.6 Clinical Criteria for Early Trial Termination

Early trial termination will be the result of the criteria specified below:

1. Quality or quantity of data recording is inaccurate or incomplete
2. Poor adherence to protocol and regulatory requirements
3. Incidence or severity of adverse drug reaction in this or other studies indicates a potential health hazard to participants
4. Plans to modify or discontinue the development of the study drug

In the event of Merck decision to no longer supply study drug, ample notification will be provided so that appropriate adjustments to participant treatment can be made.

